12.7.1.1 Overall Adverse Event Summary

An overall adverse event summary will provide, by treatment arm, the number and percentage of patients with at least:

- One TEAE,
- One TEAE related to IMP,
- One confirmed or suspected COVID-19 TEAE (as defined in [Section 10.21.2](#)),
- One TEAE leading to permanent IMP discontinuation,
- One TEAE related to IMP leading to permanent IMP discontinuation,
- One serious TEAE,

- One serious TEAE related to IMP,
- One TEAE with outcome of death,
- One AE with outcome of death related to IMP,
- One TEAE of special interest.

This table will also present the number of TEAEs and the number of TEAE of special interest by treatment arm.

12.7.1.2 All-causality Treatment-emergent Adverse Event Summary

Descriptive presentations of TEAEs will be given by PT and SOC for the Safety Analysis Set. The number and percentage of patients reporting at least one TEAE within a given treatment arm will be provided as described below

- *All TEAEs by SOC and PT,
- *All TEAEs by SOC, PT and subgroups (as described in Table 12.7-1),
- Most common TEAEs (incidence $\geq 5\%$ in either treatment arm) by SOC and PT,
- Most common TEAEs (incidence ≥ 2 patients in either treatment arm) by SOC and PT,
- Most common TEAEs (incidence ≥ 2 patients in either treatment arm) by SOC, and PT and subgroups (as described in Table 12.7-1),
- All TEAEs by SOC, PT and maximum severity,
- All TEAEs by SOC, PT and worst action taken on study drug,
- All TEAEs by SOC, PT and time of first onset of AE categorized as:
1-7 day, 8 to 14 days, 15 to 21 days and > 21 days (as described in [Section 10.21.3](#)),
- All TEAEs by SOC, PT and AE duration, categorized as:
1-7 day, 8 to 14 days, 15 to 28 days, 29 to 42 days, 43 to 61 days, > 61 days, ongoing, indeterminate (as described in [Section 10.21.4](#)),
- All TEAEs by SOC, PT and relationship to IMP,
- All treatment-related TEAEs by SOC and PT and maximum severity,
- *All treatment-related TEAEs by SOC and PT and subgroups (as described in Table 12.7-1),
- *All treatment-related TEAEs leading to permanent IMP discontinuation by SOC and PT,
- *All TEAEs leading to permanent IMP discontinuation by SOC and PT,
- *All TEAEs leading to permanent IMP discontinuation by SOC and PT and subgroups (as described in Table 12.7-1),
- All treatment-related TEAEs leading to permanent IMP discontinuation by SOC and PT and maximum severity,
- All non-serious TEAEs by SOC and PT,
- All most common non-serious TEAEs (incidence $\geq 5\%$ in either treatment arm) by SOC and PT.

**These tables will also present the total number of AEs by treatment arm and as appropriate by category of subgroup.*

12.7.2 Death, Serious Adverse Events and Other Significant Adverse Events

12.7.2.1 Death

All deaths recorded in the EDC as adverse events, as the result of an adverse event or as fatal outcome of an adverse event will be listed and summarized as described in [Section 12.7.1](#) and described in depth as narrative.

Descriptive presentations of fatal TEAEs will be given by PT and SOC for the Safety Analysis Set. The number and percentage of patients reporting at least one fatal TEAE within a given treatment arm will be provided as described below:

- All TEAEs leading to death by SOC and PT (if at least 2 patients experienced a fatal issue TEAE),
- All treatment-related TEAEs leading to death by SOC and PT (if at least 2 patients experienced a fatal issue TEAE related to study drug).

These tables will also present the total number of AEs by treatment arm.

12.7.2.2 Serious Adverse Events

Descriptive presentations of serious TEAEs will be given by PT and SOC for the Safety Analysis Set. The number and percentage of patients reporting at least one serious TEAE within a given treatment arm will be provided as described below:

- All serious TEAEs by SOC and PT,
- All serious TEAEs by SOC, PT and subgroups (as described in Table 12.7-1),
- All serious TEAEs leading to permanent IMP discontinuation by SOC and PT,
- All serious treatment-related TEAEs by SOC and PT,
- All serious treatment-related TEAEs by SOC and PT leading to permanent IMP discontinuation by SOC and PT,

These tables will also present the total number of AEs by treatment arm and as appropriate by category of subgroup.

12.7.2.3 Adverse Events of Special Interest

An adverse events of special interest (AESI) is any adverse event of scientific or medical interest to the study medication. The types of AESIs which will be analyzed are presented in **Descriptive presentations of AESIs** will be given for each AESI category on the safety analysis set presenting:

- The number and percentage of patients with at least one treatment-emergent AESI,
- The number and percentage of patients with at least one treatment-emergent AESI by SOC and PT,
- The number and percentage of patients with at least one severe treatment-emergent AESI,
- The number and percentage of patient with at least one serious treatment-emergent AESI,
- The number of and percentage of patients with at least one treatment-emergent AESI leading to permanent IMP discontinuation,
- The number of treatment-emergent AESI,
- The number of severe treatment-emergent AESI,
- The number of serious treatment-emergent AESI,
- The number of treatment-emergent AESI leading to permanent IMP discontinuation,
- The number of unique* treatment-emergent AESI,
- The number of unique* severe treatment-emergent AESI,
- The number of unique* serious treatment-emergent AESI,
- The number of unique* treatment-emergent AESI leading to permanent IMP discontinuation,
- The time to first onset of treatment-emergent AESI categorized as :1-7 day, 8 to 14 days, 15 to 21 days, 21 to 28 days and > 28 days (as described in [Section 10.21.3](#)),

**Unique AESI is defined as any AESI coded with the same PT and having the same date of onset.*

Analysis of time to first onset of AESIs will be conducted by actual treatment arm on the Safety Analysis SAS using the SAS® LIFEEST procedure.

Assuming no carry over effect, Kaplan-Meier plots (estimates) of cumulative incidence of first onset of AESI will be provided by actual treatment arm on the Safety analysis set. The time to AESI onset (in days) is defined as the number of days from 1st IMP intake of the treatment arm (e.g., nabiximols, placebo) the AESI is emergent to (as defined in [Section 12.7.1](#)) until the onset of the AESI (see detailed in [Section 10.21.4](#)).

For patients not known to have experienced an AESI during respectively Period 1 and Period 2:

- Period 1 censoring day is the date of 1st IMP intake during Period 2 minus 1 day for those patients continuing in Period 2 and, the end of study date for those patients who discontinued before Period 2,
- Period 2 censoring day is the end of study date in the period.

Additionally, for lost to follow-up patients:

- Period 1 censoring day is the earliest date between end of study date in the period and the planned Visit 6 day minus 1 day (Day 30),
- Period 2 censoring day is the earliest date between end of study date in the period and the planned Visit 10 day (Day 58).

To accompany the Kaplan-Meier (KM) plots, summary tables will display the KM estimates of cumulative probabilities (with 95% CI calculated based on the Greenwood method when applicable).

- of patients with an event at a specific time point such as 7, 14, 21, 28 (if applicable) days after 1st IMP intake in the studied period;
- time to first event based on the 10th, 20th, 30th, 40th, 50th (median) and 75th percentiles.

If the estimate of lower bound of the 95% CI is below '0' or the estimate of the upper bound of the 95% CI is over '1', then it will be respectively restricted to '0' and '1'.

The number of patients at risk along with the number and percentage of patients censored and with an event, using the number of patients at risk as denominator to calculate the percentage will also be displayed.

Each Kaplan-Meier plot (estimates) will only be provided if more than 5 patients are presenting an event in each treatment arm.

12.7.3 Laboratory Data

The clinical safety laboratory data (hematology and biochemistry) are planned to be collected at Screening and D21 of each treatment period. In case of premature end of treatment the latest assessment collected on-treatment will be used as described in [Table 10.1-1](#).

For the purposes of summarization in both the tables and listings, all laboratory values will be converted to standardized units. The investigator and medical monitor will be provided with a list of the normal ranges used by the central clinical laboratory for all variables assayed during the trial and a statement of accreditation (or similar) for the laboratory. However, AST, ALT, GGT, ALP and total bilirubin will be summarized using SI units.

Only scheduled laboratory parameters defined in Appendix 2 and those derived from them as eGFR (as defined in [Section 10.13](#)) will be included in summary tables and figures. However unscheduled laboratories values (coming from central or local laboratories) will be used in abnormality summary tables and will be presented in listings (using categories as defined in Appendix 6).

Baseline (Screening), D21 of each treatment period and the change from baseline to D21 (end of the treatment) will be summarized using the safety analysis set, by treatment arm, separately for red blood cells parameters and white blood cells parameters, hepatobiliary parameters, renal parameters, coagulation parameters and electrolytes and proteins (as described in [Appendix 2](#)). Furthermore, AST, ALT, GGT, ALP and total bilirubin will also be summarized as a multiple of the upper limit of normal (ULN).

Laboratory hematology and biochemistry (as described in Appendix 2) abnormalities will be evaluated, on patients from the Safety Analysis Set using shift tables at D21 according to baseline status with categories based on:

- reference ranges as either normal, below the lower limit of normal (LLN) as “Low” or above the ULN as “High”,
- based on CTCAE toxicity grade using version 5.0 or higher (as defined in Appendix 4 for hematology parameters and in Appendix 5 for biochemistry parameters), presented by treatment arm.

Shift tables based on reference ranges will also be repeated for the subgroups presented in Table 12.7-1.

Furthermore, a summary of patients with laboratory values outside the reference ranges at baseline and during each 21-day on-treatment safety period (as defined in [Section 10.1.1](#)) will be presented for scheduled parameter including either scheduled visit only or scheduled and unscheduled visits, by treatment arm.

Scatterplot presenting baseline against last on-treatment value within each treatment period will be presented by treatment arm for scheduled biochemistry and hematological parameters of interest.

Regarding AST, ALT, GGT, ALP and total bilirubin these parameters will be summarized by treatment arm within the Safety Analysis Set for D21 of each treatment period using SI units and as a proportion of the population with no missing assessment if abnormal values with reference to ULN are presented using the All laboratory values will be listed and all test values outside the normal range will be flagged.

Urinalysis results will be summarized and listed.

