10.1.3 Target Days and Visit Window

Visit windows are summarized in [Table 10.1-3](#) for efficacy data and urine drug screen collection and, in [Table 10.1-2](#) for all other safety endpoints.

When there are multiple observations within a visit window, the value closest to the target day will be analyzed (as described in [Table 10.1-1](#)).

For safety assessments, on-treatment assessments will be preferred to off-treatment ones.

In case of ties between observations located on different sides of the target, the observation with the earliest date/time will be used. In case of ties between observations located on the same side of the target, (i.e., more than one value for the same day but at different time), the observation with the earliest date/time will be used. However, in case of non-respect of wash-out period, the one done at least 7 days after last Period 1 dosing date will be preferred.

For efficacy, PRO endpoints visit windowing will apply whether patient is on or off treatment.

Table 10.1-1 Longitudinal Assessment – Analysis Day and Target Day

Treatment Period	Visit / Day	Analysis visit	Target Day (defined by period)	Observation used for analysis, if more than one exists
Screening	Visit 1 / Day -28 to -1	Screening	Day -28 to -1	Latest value
Period 1	Visit 2 / Day 1	Day 1	Day 1*	Closest to Target Day But Day 1 H0 should be before 1 st IMP intake and D1H3 should be post IMP intake
	Visit 3 / Day 8	Day 8	Day 8	Closest to Target Day
	Visit 4 / Day 15	Day 15	Day 15	Closest to Target Day
	Visit 5 / D21	D21	D21	Closest to Target Day
Period 2	Visit 6 / Day 31	Day 1	Day 1*	Closest to Target Day But Day 1 H0 should be before 1 st IMP intake and

Treatment Period	Visit / Day	Analysis visit	Target Day (defined by period)	Observation used for analysis, if more than one exists
				D1H3 should be post IMP intake.
	Visit 7 / Day 38	Day 8	Day 8	Closest to Target Day
	Visit 8 / Day 45	Day 15	Day 15	Closest to Target Day
	Visit 9 / Day 51	D21	D21	Closest to Target Day
Follow-up	Visit 10 / Day 58	Day 28	Day 28**	Closest to Target Day

H = Hours; IMP = Investigational medical product.

** Day 1 is based on the date of IRT call within each period*

*** Day 28 relative to the period where IMP is permanently discontinued thus visit is expected between Day 25 and Day 31*

Table 10.1-2 Longitudinal Assessment – Target Day and Visit Window – Part 1

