Treatment Period	Visit / Day	Physical examination / 12-lead ECG / Clinical laboratory blood sampling	Target Day (defined by period)	Examination of oral mucosa / C-SSRS	Body weight / Serum urine pregnancy test	Vital signs	Dipstick urine
Screening	Visit 1 / Day - 28 to -01	Day 28 – D1H0	Day 28 to -01	Day 28 to -01	Day 28 to -01	Day 28 to -01	Day 28 – D1H0 (before 1st IMP dosing)
Period 1	Visit 2 / Day 1H0	Day 1*	Day 1H0 *	Day 1H0 (before P1 IMP intake)	Day 1 H0 (before P1 IMP intake)	Day 1 H0 (before P1 IMP intake)	Day 1 post dose (the day of 1st P1 IMP intake)
	Visit 2 / Day 1	Day 1 H2- H4*					Day 2 (day following IMP intake) – Day 18
	Visit 4 / Day 15	Day 15		Day 1 post dose to Day 18			Day 19 to LP1V
	Visit 5 / D21	D21	Day 1 post dose to LP1V	Day 19 to LP1V			
	Wash-out						
Period 2	Visit 6 / Day - 31	Day 1H0*		Day 1 – 4 days to D1H0 *	D1H0 (before P2 IMP intake)	Day 1 – 4 days to D1H0	Day 1 post dose (the day of 1st P2 IMP intake)
	Visit 6 / Day - 31	Day 1H2- H4*					Day 2 (day following IMP intake) – Day 18
	Visit 8 / Day 45	Day 15		Day 1 post dose to Day 18			Day 19 to LP2V
	Visit 9 / Day 51	D21	Day 1 post dose to LP2V	Day 19 to LP2V			
	Follow-up	Visit 10 / Day 58	Day 28***		after last IMP dosing	After last IMP dosing	Day 1 post 1st IMP dosing to after last IMP dosing

H = Hour; P = Period; LP1V = Last visit during Period 1, LP2V = Last visit during Period 2, IMP = Investigational Medical Product; IRT = Interactive response technology; ECG = Electrocardiogram; C-SSRS = Columbia-Suicide Severity Rating Scale.

* Day 1 is based on the date of IRT call within each period.

*** Day 28 relative to the period where IMP is permanently discontinued.

Table 10.1-3 Longitudinal Assessment – Target Day and Visit Window – Part 2

Treatment Period	Visit / Day	Target Day (defined by period)	Urine drug screen	11-point NRS spasticity / Daily spasm count	MAS	MSSS-88	T25FW test
Screening	Visit 1 / Day - 28 to -01	Day -28 to -01	Day -28 to -01	Day -28 to -01	Day -28 to -01		
Period 1	Visit 2 / Day 1H0	Day 1*	Day 1 H0 (before P1 IMP intake)	Day1H0 (before P1 IMP intake)*	Day1H0 (before P1 IMP intake)	Day 1H0 (before P1 IMP intake)	Day 1H0 (before P1 IMP intake)
	Visit 2 / Day 1	Day 1 H2- H4**			Day1 post dose (the day of 1 st P1 IMP intake)** up to Day 18		
	Visit 4 / Day 15	Day 15		Day 2 (day following IMP intake) – Day 18 (or the first day of maintenance phase)			

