12.7.5.3 Columbia-Suicide Severity Rating Scale

The Columbia-Suicide Severity Rating Scale is a patient questionnaire that evaluates suicidal ideation and behaviors. In this study, the C-SSRS is assessed at Screening using the "Baseline/Screening Version" and at subsequent timepoints using the "Since Last Visit" version. At the Screening visit, patient eligibility will be assessed with respect to suicidal ideation during the past month and suicidal behavior during the past 5 years.

The C-SSRS questionnaire is planned to be administered by the investigator (or designee) at Screening, Day 1 H0, Day 15 and D21 of each treatment period and at FU.

To analyze these questionnaires, events will be considered associated with:

- Nabiximols, if collected between first and last date of nabiximols intake.
- Placebo, if collected between first and last date of placebo intake.
- Any unscheduled C-SSRS questionnaire taken during the wash-out period will be linked to the actual treatment arm defined during Period 1.

- FU if collected after last IMP intake and only the latest one will be used for summary.

Derived parameters are presented in [Section 10.23](#).

On treatment and by timepoints assessments

The number and percentage of patients who have answer “Yes” to each of the 5 suicidal ideation subtypes and each of the 5 suicidal behavior subtypes along with the number and percentage of patients presenting:

- A suicidal ideation,
- A suicidal behavior,
- A suicidal ideation or behavior,
- A self-injurious behaviour without suicidal intent.

will be summarized at baseline, for each scheduled on-treatment timepoint, for the 51-day safety on-treatment period, for last on-treatment assessment and for the Follow-up assessment by treatment arm. For this summary FU assessments will be linked to the last treatment received.

Shift table from baseline to maximal suicidal ideation score as well as a shift table for change in category (no suicidal ideation or behavior, suicidal ideation [without suicidal behavior], suicidal behavior) will also be summarized by treatment arm for patients having a baseline and at least 1 post baseline on-treatment assessment.

The number and percentage of patients presenting a suicide-related treatment-emergent event defined as:

- A treatment emergent suicidal ideation (without suicidal behavior) compared to recent history,
- A treatment emergent serious suicidal ideation compared to recent history,

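### The D21 laboratory shift tables can show a transient high-grade abnormality at its lower D21 grade, and for non-hepatic parameters no by-treatment table gives the worst on-treatment CTCAE grade

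*SAP*

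**What the plan says.** SAP 12.7.3 states that haematology and biochemistry samples "are planned to be collected at Screening and D21 of each treatment period". Abnormalities are then evaluated "using shift tables at D21 according to baseline status with categories based on" two classifications: low, normal or high against the reference range, and a second one "based on CTCAE toxicity grade using version 5.0 or higher", with the grades set out in Appendices 4 and 5.

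The D21 value is chosen under SAP 10.1.3. Table 10.1-2 gives the Period 1 D21 laboratory window as "Day 1 post dose to LP1V", and Period 2 is analogous. Within a window the rule is: "When there are multiple observations within a visit window, the value closest to the target day will be analyzed". Two qualifications apply. One is in 10.1.3: "For safety assessments, on-treatment assessments will be preferred to off-treatment ones". The other is in 12.7.3: after premature end of treatment, the latest on-treatment assessment is used.

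Section 12.7.3 also says that unscheduled central or local results feed the abnormality summaries and the listings, using the Appendix 6 categories. It plans a by-treatment summary of patients with "laboratory values outside the reference ranges at baseline and during each 21-day on-treatment safety period", in one version with scheduled visits only and one that adds unscheduled visits. All values are listed and out-of-range values are flagged.

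**The concern.** Because there is one scheduled post-dose sample per period, anything that appears and resolves before Visit 5 or Visit 9 can be detected only on an unscheduled sample, which will often be one taken because something was suspected. A rule that keeps the value nearest Day 21 sets that sample aside whenever a Day 21 on-treatment sample exists. The graded shift table is where a reader would look for laboratory severity by treatment, and laboratory change is a secondary safety endpoint.

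The SAP is less restrictive elsewhere. Repeated AEs are counted at worst severity (12.7.1). The liver plot uses maximal ALT and bilirubin (12.7.3.1). Weight abnormality uses every measurement, scheduled or not (12.7.5.1). For suicidality there is a "Shift table from baseline to maximal suicidal ideation score" (12.7.5.3). No reason is given for handling graded laboratory toxicity differently.

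**Working it through.** There is no stated figure to reproduce. The check applies the SAP's selection rules by hand to example patients and then looks for each abnormality in every other planned laboratory output. The laboratory values are assumed; the grade limits come from SAP Appendices 4 and 5.

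**Selection.** For a sample on day t, the distance to target is |21 − t|. A Day 10 sample has distance 11 and a Day 21 sample has distance 0, so the Day 21 value is used if both are on treatment.

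| Example | Day 10 (unscheduled) | Day 21 | Grade in D21 shift table | Other planned outputs |
|---|---|---|---|---|
| (a) Neutrophils | 0.4 × 10⁹/L: Grade 4 (<0.5) | Normal | No toxicity | Out-of-range summary with unscheduled visits; listing. No grade |
| (b) Potassium | 6.5 mmol/L: Grade 3 (>6.0 to 7.0) | Normal | No toxicity | As (a) |
| (c) ALT, normal baseline | 6 × ULN: Grade 3 (>5 to 20 × ULN) | Normal | No toxicity | As (a), plus Appendix 6 categories >3 × and >5 × ULN, and the DISH maximum |
| (d) ALT as (c), IMP then stopped, all later samples off treatment | 6 × ULN: Grade 3 | Off treatment | Grade 3 | As (c) |

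In (d) the Day 10 value is the latest on-treatment one. SAP 10.1.1 adds 0 days to the on-treatment safety period for laboratory data, so the later samples count as off treatment. If the Day 21 value in (a) to (c) were mildly abnormal, the table would show that lower grade instead of no toxicity.

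**Dependence on the window.** The layout of Table 10.1-2 is hard to follow in the text version, but the result does not rest on it. If the window includes Day 10, the closest-to-target rule selects Day 21. If the window is narrower, Day 10 falls outside it.

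**What remains for non-hepatic parameters.**
- The any-time summary in 12.7.3 records only that a value was out of range. A neutrophil count just below the lower limit and a Grade 4 count are the same entry.
- The laboratory thresholds in Appendix 6 cover ALT, AST, ALP, total bilirubin and GGT only.
- The DILI table and DISH plot in 12.7.3.1 concern the liver.
- Listings show the value but make no comparison by treatment.

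The Appendix 4 and 5 grades for haematology, electrolytes and creatinine therefore reach a by-treatment table only through the D21 shift.

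**Unscheduled values.** Section 12.7.3 does not say whether the CTCAE shift tables are among the abnormality summaries that use unscheduled results. Even if they are, the closest-to-target rule would still select Day 21 in (a) to (c). Admitting those samples without changing the rule does not close the gap.

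**The case against.** The strongest reply is that most of the information is reported. A reader might infer that a severe early abnormality is reported as no toxicity, or that suspicion-driven samples are dropped. The documents do not support either reading. The abnormality is counted by arm in the out-of-range summary with unscheduled visits and is flagged in the listings. Liver values are captured at any post-baseline visit and at their maximum. The no-toxicity cell applies only in the D21 tables, and only if the D21 value is itself Grade 0. A value after which IMP is stopped can enter the shift table at its own grade, as in example (d).

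There is also an AE route. Protocol 9.2.12 requires laboratory results considered to represent an AE to be recorded, and SAP 12.7.1 tabulates TEAEs by arm at worst severity. This stands as a partial safeguard. It depends on investigator judgement, and it uses mild, moderate or severe, which is not the CTCAE grade.

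Protocol 13.6.6.3 asks for shift tables of values outside the normal range and requires neither CTCAE grading nor a worst-value table. The plan therefore meets the protocol, and the addition is an improvement, not a correction of non-compliance. The comparison with vital signs and the C-SSRS is also weaker than it looks, because those have several scheduled assessments per period. The comparison with weight, where unscheduled measurements are expressly included, holds.

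**Conclusion.** The point holds in a limited form. The reference-range and CTCAE shift tables can understate a transient abnormality whose on-treatment D21 value is better. For haematology, electrolytes and creatinine, no other by-treatment table supplies the worst on-treatment grade. This is a safety-display gap with no bearing on efficacy inference.

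Its size in this trial cannot be estimated. The documents give no rate of abnormality or of unscheduled sampling, and any calculation of the share of episodes missed would rest on invented onset times and durations. For scale only: SAP 8.2 records a recommendation of 68 completers, each of whom receives both treatments, so one patient is 1/68 ≈ 1.5% of a treatment arm. A single Grade 3 or 4 case moved to a lower grade would be visible.

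The conclusion assumes that the closest-to-target rule governs the D21 shift tables, which is the plain reading of 10.1.3 and 12.7.3 together.

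**What to change.** In SAP 12.7.3:

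1. Add a shift table from baseline to worst on-treatment CTCAE grade for each 21-day on-treatment safety period, by treatment arm, using scheduled and unscheduled results from central and local laboratories. Where a parameter is graded in both directions, show worst low and worst high separately.
2. Keep the D21 shift tables beside it.
3. State that the worst-grade table is one of the abnormality summaries that use unscheduled values.

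The cost is a few lines of SAP text and an additional derived record per parameter, direction and period. No new data are needed. The downside is that unscheduled sampling is symptom-driven, so a worst-value table also reflects how often each patient was sampled. Presenting the D21 table alongside lets the reader see both.
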